7.1.5.4. Grouping Time

Before eligible for inclusion, it is necessary for the agreement by the subject and sign the informed consent, and then carry out inspection:

- 1) General data of subjects, and vital signs;
- 2) Past treatment history, clinical diagnosis and past treatment;

If it complies with the inclusion criteria of the current research rather than the exclusion criteria, after making preparation before the treatment, it shall take the occluder implanting time by surgery as the grouping time point.

7.1.5.5. Expected overall sustainable time for clinical trial and its determination reason

Adoption of NiTi alloy woven for VSD occluder with VSD occlusion operation has been widely applied for over one decade, and the operating techniques and clinical follow up research have been very mature, the completely degradable occluder in the current trial has not been changed in the basic structure, operating mechanism for VSD occluder compared with the traditional VSD occluders.

According to the past products already received the registration certificate and their application already proven their safety, literature references both home and abroad are generally taking 6 months as the limits for short term efficacy evaluation of occluder, and the residual shunts after occluder implanting are mainly concentrated in the first 3 months after operation. Animal trial research demonstrate, the occluder has already been in complete endothelialization within 3 months after occluder implanting, taking into account of the long term observation for validity and safety of products after implanting into human body, therefore, the current clinical trial selects 6 months as the follow up time for clinical trial.

7.1.5.6. Expected participating sustaining time for each subject

The duration from the subjects signing the informed consent, grouping, operation to follow up completion are about 7 months, and the primary endpoint for follow up completion as the conclusion of the trial, and it is further follow up to 3 years after trial completion.

7.1.5.7. Subject number necessary for clinical trial

It is expected of 108 subjects for inclusion, respectively of 54 cases in the trial group and control group.

7.1.6. Effective Evaluation Method

I. Effective parameter explanation

Primary Efficacy Indices: 6 months occlusion success rate.

6 months occlusion success (definition): 6 months occlusion success refer to ultrasonic cardiogram inspection in follow up 6 months after operation, there is no residual shunts in the occlusion location or only with minor amount of residual shunts.

Secondary Efficacy Indices: Surgical Technical Successful Rate.

Surgical Technical Successful Rate (Definition): Surgical intervention delivery devices through the occluder (trial group) or occluder intervention delivery devices (control group) implanting the occluder and then safely released.

Secondary Efficacy Indices: Technical Successful Rate.

Technical Successful Rate (Definition): Surgical intervention delivery devices through the occluder (trial group) or occluder intervention delivery devices (control group) implanting the occluder and then safely released, without occluder shedding during operation.

II. Evaluation, recording and analysis of effective parameter method and time selection

Immediate, 1 month, 3 months, 6 months occlusion success after intervention occlusion operation, namely ultrasonic cardiogram suggesting the residual shunt bunch diameter no higher than 2mm, according to the Doppler shunts signal from left to right judgment, it is better in effect to have no shunts signal from left to right; with diameter lower than 1mm from left to right shunts signal as trace amount of residual shunts; with diameter between 1 and 2mm as minor amount of residual shunts.

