3.2. Content

The trial is “The clinical trial for safety and efficacy in clinical application of completely degradable ventricular septal defect occlusion system”, as a perspective, multiple-centered, randomized control non-inferiority clinical trial with the 6 month occlusion successful rate of completely degradable occluder after occlusion as the primary evaluation indices, and with the ventricular septal defect occluder and the occluder intervention delivery devices manufactured by the company as the control. It is

estimated that there are 108 cases (54 pairs) of subjects included in the 4 central groups nationwide between December, 2018 and December, 2019, during the treatment courses, it is randomly applied the completely degradable occluder system and occluder surgical intervention delivery devices manufactured by Shanghai Shape Memory Alloy Co., Ltd or ventricular septal defect occluder and occluder intervention delivery devices already marketed, and carry out clinical follow up instantly after operation, one month after operation, three months after operation, and six months after operation. After completion of 6 months clinical follow up, it is carried out clinical summarization, used in the registered application for products.

4. The Background Materials for Clinical Trial

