7.1.2. Trial Method Selection and Their Rationale

The current trial applied perspective, multiple centered, randomized controlled non-inferiority clinical trial. It is evaluated of the safety and efficacy of completely degradable occluder system in clinical application, with the ventricular septal defect occluder manufactured by Shanghai Shape Memory Alloy Co., Ltd as the clinical trial control product. It is evaluated of the safety and efficacy of occluder surgical intervention delivery devices in clinical application, with the occluder intervention delivery devices manufactured by Shanghai Shape Memory Alloy Co., Ltd as the clinical trial control product. The primary endpoint index for evaluating occluder surgical intervention delivery devices is that it can be released when the occluder is delivered to the lesion location during operation; and the primary endpoint index for evaluating completely degradable occluder system is the success rate at month 6, which is evaluated for efficacy through ultrasonic cardiogram.

7.1.3. Measures for reduction and avoidance for deviation.

- 1) Before research initiation, the sponsor should carry out relevant training for researchers participated in the current research, and ensuring that the researchers sufficiently understand the research flow, and skillful in the operation of research instruments; during the course of research, the researchers should carry out operation strictly according to the operating methods and specification in the research protocol, and the clinical research monitor should do well of the quality control and monitoring work, and ensure that the researchers carry out operation and implementation strictly according to the research protocol. It is implemented of the measures mentioned above during the entire research procedures, to reduce the losses or operation errors;
- 2) It applied strict randomized trial design, to avoid the selection deviation in treatment. After the trial started, when the subjects meet the inclusion criteria for testing, the researchers shall log on to the central randomizing system for randomized grouping.

- 3) Subjects are screened for inclusion and exclusion strictly according to the clinical diagnostic criteria in trial protocol, to reduce the selection deviation;

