7.1.5.3. Standards and Procedures for the stop of trial/test treatment

Falling off standard:

All the subjects filling out the informed consent and qualified in screening for enrollment into randomized research, when they withdraw from the trial research in any time for any reasons, so long as they failed to accomplish the observation cycle prescribed by the protocol, they shall be deemed as falling off cases, and stop the trial. Common falling off causes include:

- (1) Occurrence of serious adverse events resulted in the furthering completion of the trial;
- (2) Changes in diseases conditions, unsuitable for furthering completion of the trial;
- (3) Loss of follow up;
- (4) The patients or their family members demanding withdrawal from the trial;
- (5) Incapable of furthering completion of the trial for any other reasons;
- (6) The subjects are poor in compliance, influencing the efficacy and safety judgment.

After the subjects' falling off, the researcher must contact the subjects for all possibilities, and ask for the reasons and accomplish all the assessment items possible of completion. When the patients withdraw due to the allergic reaction, adverse reactions, and invalid treatment, the researchers must adopt the corresponding treatment measures according to the actual conditions of the subjects.

Rejecting Criteria:

All the cases already included however comply with any of the following conditions, must be rejected:

- (1) Misdiagnosis (without application of any testing instrument);
- (2) Patients without any testing records (without application of testing instrument);
- (3) Patients incompliance with the inclusion/exclusion criteria (without application of testing instrument);
- (4) Due to the application of any forbidden drug, which results in the incapability for effective evaluation (without application of testing instrument).

For rejection cases it must be explained for the reasons, and their CRF Table must be preserved and ready for review. Without treatment statistical analysis, however after receiving

treatment, with at least one effectiveness and safety records, the patients can participate in the safety analysis according to conditions.

Standards/Procedures for the stop of trial/test treatment:

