8.9 Selection Standard and Causes for subjects included into the analysis

Statistical analysis shall be based on the foundation of the following analysis population, before the initiation of statistical analysis, it would make clear definition for the analysis population, which include:

Full Analysis Set (FAS): The subject set defined according to the Intention To Treat Principle, referred to the data set of all the subjects participated in randomization and applying research devices. For patients fail to observe of the primary efficacy indices, it is planned to apply WCCF (Worst Case Carry Forward) strategy to carry out cutting and transfer for the missing data.

Per-protocol population set (PPS): Refer to all the treatment population subgroup finished the trial and excluded the severe breach of protocol (refer to research subject breaching the inclusion criteria or in compliance with the exclusion criteria, etc).

The primary efficacy indices analysis shall be carried out on the basis of Full Analysis Set and Per-protocol population set at the same time; in addition, all the baseline demographic data and secondary efficacy analysis shall be carried out on the basis of Full Analysis Set, and the safety evaluation shall also be carried out on the basis of Full Analysis Set (Therefore, it would not define SS separately).

8.10 During validation of hypothesis, it is excluded of specific information and their causes (if applicable)

Not applicable.

9. Data Management

It applies Electronic Data Capture(EDC) to complete the collection of trial data.EDC system has undergone strict testing, completely meet the requirements of “Quality Management Norm for Clinical Trial of Medical Devices”, “Data Management Work Technique Guideline for Clinical Trial”.Before the online of the system, it is necessary to carry out training and testing for the relevant application staff, to ensure that the system meet the requirement of the trial.After formal online, relevant staff would obtain the account and password.The account binds the roles and authority of the clients, and they should properly preserve the account information, and forbidden to divulge the account information to any others, or replace others in their performance of others rights.

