13.4 Forecast and measures of serious adverse events

The following complications may occur during surgical intervention of the occluder: arrhythmia, displacement or detachment of the occluder, rupture of chordae tendineae, tricuspid insufficiency, aortic regurgitation, residual shunt, hemolysis, and acute myocardial infarction.

1) Arrhythmia

There may be ventricular premature beat, ventricular tachycardia, bundle branch block and atrioventricular block during the operation, which usually disappear after changing the position and direction of guide wire, catheter and delivery sheath without special treatment. Ventricular fibrillation is rare, and electrical cardioversion shall be performed immediately once it occurs. Temporary cardiac pacemakers should be installed when the ventricular rate is too slow and the Adam-Stoke syndrome occurs. If no recovery is found after 3 weeks, permanent pacemakers shall be installed.

2) The occluder is displaced or falls off

It is related to small size of occluder and improper operation. If the occluder falls off, the bedside X-ray chest radiograph shall be performed immediately to confirm the location of the occluder. Meanwhile, it shall be extended upward along the original surgical incision. The occluder shall be removed and VSD repaired under extracorporeal circulation through the conventional median sternal incision.

3) Rupture of chordae tendineae

Surgical VSD occlusion is performed under the tricuspid valve without establishing a strongly supported sheath delivery track across the tricuspid valve. The incidence of tricuspid valve chordae tendineae ruptures is much lower than that of conventional percutaneous occlusion, because the latter can cause chordae tendineae ruptures if the guide wire passes through the chordae tendineae after the track is established. If rupture of chordae tendineae occurs, it shall be treated under extracorporeal circulation.

4) Tricuspid insufficiency

The incidence rate is 1.6%, which was related to defect location, operation mode and occluder size. The posterior septal VSD is closely related to tricuspid valve, which can cause obvious tricuspid regurgitation after the occluder is implanted. When releasing the occluder, the distal end of the sheath shall be pushed close to the occluder before rotating the push rod to prevent entanglement with the chordae tendineae. The edge of the occluder is too long, especially when

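### Six-month success rests on residual shunt alone, so a patient whose occluder detached and whose defect was then repaired surgically can count as a success

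*Combined protocol and SAP*

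**What the plan says.** Section 7.1.6 defines the primary endpoint by the 6-month echocardiogram: "there is no residual shunts in the occlusion location or only with minor amount of residual shunts". Its second part sets the threshold at a residual shunt of no more than 2 mm. Section 7.1.2 describes the endpoint in the same way, as "the success rate at month 6, which is evaluated for efficacy through ultrasonic cardiogram". Sections 8.1.1 and 8.5 add no further condition.

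Loss of the device appears in only one efficacy index, the secondary Technical Successful Rate, and only within the procedure: "implanting the occluder and then safely released, without occluder shedding during operation".

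Section 13.4 lists displacement or detachment among the expected complications and states what follows a detachment: "The occluder shall be removed and VSD repaired under extracorporeal circulation through the conventional median sternal incision". For haemolysis, the same section also foresees surgical removal or a second closure device.

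Three other rules could bear on such a patient:

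- Falling off (Section 7.1.5.3) concerns subjects who do not complete follow-up: "so long as they failed to accomplish the observation cycle prescribed by the protocol, they shall be deemed as falling off cases".
- Worst-case imputation in the Full Analysis Set (Section 8.9) is for unobserved outcomes: "For patients fail to observe of the primary efficacy indices, it is planned to apply WCCF".
- The Per-protocol Set (Section 8.9) is "all the treatment population subgroup finished the trial and excluded the severe breach of protocol". Section 8.4 adds that concomitant treatment affecting efficacy counts towards the falling-off rate.

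**The concern.** A detachment that leads to open repair is a failure of the device under test. A surgeon's repair should leave little or no shunt at six months, so the echo criterion is likely to be met for a reason unrelated to the occluder. The primary endpoint would then credit the device with the result of the operation that replaced it.

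The coding would also depend on chance. If the 6-month echo is done and clean, the patient is a success. If it is missing, worst-case imputation most naturally gives a failure. In the Per-protocol Set the patient is a success or is excluded, and a failure under neither reading.

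In a non-inferiority trial with a 98% assumed success rate, very few failures carry the comparison. Hiding one in the trial arm makes non-inferiority easier to claim; hiding one in the control arm makes it harder.

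**Working it through.** **1. The patient traced through the rules.** Take a randomised patient who receives the occluder, has a detachment after the operation and a surgical repair, and stays in follow-up.

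| Rule | Effect |
|---|---|
| Success definition, 7.1.6 | Echo shows shunt of 2 mm or less: success |
| Technical success, 7.1.6 | Secondary, and limited to shedding during the operation |
| Falling off, 7.1.5.3 | Does not apply if the 6-month cycle is completed |
| Worst-case imputation, 8.9 | Does not apply, because the outcome was observed |
| Per-protocol Set, 8.4 and 8.9 | Success, or excluded |
| Blind review (9.3); optional committee for disputes (section XV) | Could notice the case, but have no coding rule |

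**2. The plan's own sample size.** Inputs from Section 8.2.1: success 0.98 in both arms, margin 0.08, one-sided alpha 0.025, power 80%, dropout 10%. With equal rates the plan's formula reduces to

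n = 2p(1-p)(1.960 + 0.842)² / 0.08² = 0.0392 × 7.849 / 0.0064 = 48.07.

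Dividing by 0.9 gives 53.4, so 54 per arm. The stated figure reproduces. Expected failures per arm are 0.02 × 54 = 1.08.

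**3. One trial-arm patient recoded from success to failure.** Section 8.5 requires the lower 95% limit to exceed -8%. The documents name no interval method, so two are shown, both unstratified with 54 per arm: Wald, and the Miettinen-Nurminen score. The Wald lower limit is

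d - 1.960 × √[pT(1-pT)/54 + pC(1-pC)/54].

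Example with 53 control successes:

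- Trial 53: 0 - 1.960 × √(0.000337 + 0.000337) = -5.09%.
- Trial 52: -0.0185 - 1.960 × √(0.000660 + 0.000337) = -8.04%.

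| Control successes | Trial successes | Wald | Score | Verdict reverses under |
|---|---|---|---|---|
| 53 | 53 to 52 | -5.09% to -8.04% | -8.17% to -10.98% | Wald only |
| 53 | 54 to 53 | -1.74% to -5.09% | -4.91% to -8.17% | score only |
| 52 | 53 to 52 | -4.34% to -7.12% | -6.53% to -9.38% | score only |
| 51 | 52 to 51 | -6.07% to -8.64% | -7.78% to -10.40% | both |

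The last row has success rates below the planned 98%.

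**4. How often one patient decides the verdict.** Fix exactly one repaired patient with a clean echo. Let the other 53 in that arm and the 54 in the other arm be binomial at 0.98, and enumerate all tables.

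- Patient in the trial arm. Wald: non-inferiority is met in 77.3% if coded success and 45.6% if coded failure, a difference of 31.7%. Score: 47.0% and 13.6%, a difference of 33.4%.
- Patient in the control arm. Coding as success turns a pass into a fail in 7.9% (Wald) or 17.8% (score).

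**5. False non-inferiority.** Suppose true device success is 90% v 98%, exactly at the margin. Add an assumed percentage of patients who are repaired and coded as successes.

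| Repaired and coded success | Wald | Score |
|---|---|---|
| none | 4.4% | 1.5% |
| 1 point, trial arm only | 6.8% | 2.5% |
| 2 points, trial arm only | 10.3% | 3.8% |
| 1 point in both arms | 4.8% | 1.1% |
| 2 points in both arms | 6.3% | 1.1% |

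The score entry for 1 point in the trial arm is 2.45% before rounding. Under the score interval, exceeding 2.5% therefore needs a trial-arm excess of more than about 1 point. Under Wald the error already exceeds 2.5% with no repaired patients, so only the increase is due to coding.

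**The case against.** **The wording implies closure by the device.** The definition refers to the occlusion location, and Section 3.2 names the endpoint as "6 month occlusion successful rate of completely degradable occluder after occlusion". After removal and open repair it is doubtful that an occlusion location exists. This probably is what the authors meant, but no rule says so, and the definition can be applied literally without contradicting anything else in the plan.

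**Details may come later.** Section 8.7 defers imputation details to a separate analysis prospectus, and Section 8.8 has that finalised before database lock. But neither section promises a coding rule for this endpoint, and the definition of a primary endpoint belongs in the protocol.

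**The route to a false success is narrow.** The patient must have a detachment and a repair, remain in follow-up, have a clean echo and be kept in the analysis. A serious adverse event or efficacy-altering treatment may lead to falling off or exclusion. This limits how often the problem arises. It does not close the gap, because exclusion is not failure.

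**Worst-case imputation is undefined.** Read as the worst echo observed, it could also give success, and Section 8.7 allows last observation carried forward. This is right. The statement that a missing echo gives failure is the natural reading, not a certain one.

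**The figures are conditional.** The documents give no event rate. The analysis in Section 8.1.2 is adjusted for centre, while these figures are unstratified. Two points in both arms puts recorded control success at 100%, which is extreme. If dropout reached 10% and were imputed as failure, it would add about 0.10 × 54 = 5.4 failures per arm to the 1.1 used here. All of this stands, and it limits the size of the effect rather than the miscoding itself.

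**Safety reporting keeps the event visible.** It does, but it does not alter the primary analysis.

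**Conclusion.** The concern holds. Followed as written, the definition can record a device failure as a success, and no other rule corrects it. This should be fixed, since the verdict can turn on a single patient.

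The size in practice is unknown. The bias favours the trial device only if such events are more frequent in the trial arm. Equal rates change the error rate little, and a lone control-arm case works against the device. The numerical results rest on 54 observed outcomes per arm, an unstratified Wald or score interval, and assumed repair rates.

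**What to change.** Define 6-month success as a residual shunt of no more than 2 mm with the assigned occluder in place and none of the following before the 6-month echo: detachment, occluder removal, surgical repair of the defect, or an additional closure device. Then:

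- Count any of these events as failure in both the Full Analysis Set and the Per-protocol Set, whatever a later echo shows.
- State that device failure alone does not exclude a patient from the Per-protocol Set.
- Judge whether the occluder is in place from recorded events, not from its visibility. Section 5.1 reports that degradation starts at about 6 months, and planned degradation must not count as failure.
- Reconcile Sections 8.4, 8.7 and 8.9, and state that worst-case imputation means failure.
- State how an abandoned occlusion (Section 13.4) is coded. The documents do not say what follows it, and no figure here includes it.

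This concerns endpoint coding only and changes no patient care. The data are already collected through the operation record, the echocardiograms, and the adverse events with their treatment and results (Sections 7.1.7 and 7.2).

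The cost is possible loss of power, because Section 8.2.1 does not say whether its 98% already means closure by the device. By the plan's formula, with 49 evaluable per arm and equal rates, power = Φ(0.08 / √[2p(1-p)/49] - 1.960):

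| Success in both arms | Power at 49 per arm | n per arm before dropout |
|---|---|---|
| 98% | 80.7% | 49 |
| 97% | 64.1% | 72 |
| 96% | 52.4% | 95 |
| 95% | 44.3% | 117 |

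The sample size should be rechecked when the wording is changed.
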